# Confidence Intervals of Difference (P1-P2)

Interval	Estimated	Confidence	Confidence
Method	Value	Limit	Limit
Chi-Square	0.2561	0.1456	0.3666

(Pearson)

(The calculation results are presented in the language of the original source)

In view of the considered nosology and absence of significant factors requiring a conservative approach for determination of the non-inferiority margin, for this purpose we can use a two-sided CI 90%. In such a case, the lower limit for the rate difference (a two-sided CI 95%) will amount to 14.6%. Therefore, a margin of 14.5% is considered to be justified.

Based on the above, we may hypothetically expect a rate of positive response to a new

	therapy (absence of a sore throat as an efficacy measure) at least 63%. A statistic hypothesis tested:		
	H0: $p_1-p_2 \le -14.5\%$ compared to H1: $p_1-p_2 > -14.5\%$ If a null hypothesis is rejected, a conclusion will be made that efficacy of the study drug is not less than that of the comparator drug.		
	A sample size is evaluated based on the following assumptions:		
	- A rate of positive response to therapy (absence of a sore throat as an efficacy measure) in a comparator drug arm is 63%.		
	- A rate of positive response to therapy (absence of a sore throat as an efficacy measure) in a study drug arm is 65% (chosen within the tested hypothesis and based on the sample size and expected positive response).		
	- Power = 80%		
	- A non-inferiority margin: 14.5		
	- Significance level: 97.5%		
	- Randomization in 1:1 ratio (study drug : comparator drug). A number of patients required at 80% power and 2.5% one-sided significance level to prove the hypothesis of the study drug efficacy not more than 14.5% inferior to that of the comparator drug (determined by absence of a sore throat after 3 days of therapy) if 128 patients in every arm.		
Interim analysis	An interim analysis may be conducted after receipt of efficacy data for Angal and ANTI-ANGIN ® FORMULA, spray, after 3 days of therapy, on Day 4, for 100 patients in every arm. The interim analysis includes demographic data, data on the anamnesis and concomitant therapy, available data on efficacy and safety of Angal and ANTI-ANGIN ® FORMULA drugs.		
Blinding, randomization	This trial will be open, without blinding. The patients will be included by randomization in 1:1 ratio using envelopes at the trial site.		

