# 4.3.2 Blinding methods

This trial will be conducted without blinding (an open trial).

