#### **Confidence Intervals of Difference (P1-P2)**

Interval	Estimated	Confidence	Confidence
Method	Value	Limit	Limit
Chi-Square (Pearson)	0.2561	0.1456	0.3666

(The calculation results are presented in the language of the original source, i.e., from NCSS 8 statistical program).

- This is a non-inferiority trial; therefore, a non-inferiority margin for the primary endpoint should be justified and amount to not more than 14.5%.
- An expected rate of positive response to therapy (absence of a sore throat as an efficacy measure) in a comparator drug arm is 63%.
- An expected rate of positive response to therapy (absence of a sore throat as an efficacy measure) in a study drug arm is 65% (chosen within the tested hypothesis and based on the sample size and expected positive response).
- A one-sided type I error ( $\alpha$ ) = 2.5 % (0.025)
- A type II error ( $\beta$ ) = 20% (0.2), which corresponds to 80% power.
- Expected discontinuation from the trial will amount to 10% during the treatment.

The tested hypotheses are worded as follows:

1. Null hypothesis (Ho): Difference in the primary endpoint achievement incidence while using Angal, the study drug, and ANTI-ANGIN® FORMULA, the original drug, for treatment of acute infectious and

inflammatory pharyngeal diseases will exceed 14.5% in favor of ANTI-ANGIN  $^{\circledast}$  FORMULA:

$$H_0: p_1 - p_2 \le -0.145$$

2. Alternative hypothesis (HA): Difference in the primary endpoint achievement incidence while using Angal, the study drug, and ANTI-ANGIN® FORMULA, the original drug, for treatment of acute infectious and inflammatory pharyngeal diseases will not exceed 14.5% in favor of ANTI-ANGIN® FORMULA

$$H_A: p_1 - p_2 > -0.145$$

Where p1 and p2 is the primary endpoint achievement incidence while using Angal, the study drug, and ANTI-ANGIN® FORMULA, the original drug, respectively.

To calculate a sample size in every group, one can use a formula presented by Chow S, Shao J, Wang H. 2008. Sample Size Calculations in Clinical Research. 2nd Ed. Chapman & Hall/CRC Biostatistics Series. page 90:

$$n = (p_1 \times (1 - p_2) + p_2 \times (1 - p_2)) \times \left(\frac{z_{1-\alpha} + z_{1-\beta}}{p_1 - p_2 - \delta}\right)^2$$

where:

- n = Size of one group;
- z = Normal distribution function at the set levels of  $\alpha$  and  $\beta$ ;
- $\delta$  = Non-inferiority margin;
- p1 = Expected proportion in Angal group;

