#### **11.3 Protocol deviations**

Protocol deviation is intended deviation from approved protocol.

Serious protocol deviation is a deviation, which may, according to the estimate by the Investigator or a person assigned by the Investigator, result into

withdrawal of the subject from the trial or withdrawal of his/her data from clinical and/or statistical parts of the trial. The deviations not referred to as serious ones shall be considered minor protocol deviations.

Serious protocol deviations should be reported as soon as possible to the Sponsor by the clinical center staff and/or CRO and Monitor (if he/she is in the center). The Sponsor can propose to reclassify the protocol deviation (minor into serious and vice versa) based on the estimate. In such a case, the classification performed by the Sponsor shall prevail and must be communication to CRO together with written rationale. The Sponsor must be informed of minor protocol deviations within 10 business days but before commencement of the next clinical period of the trial or before commencement of a clinical phase.

An exception is represented with minor protocol deviations, which can be included in the draft report on the trial:

- Logistic deviations (in time from the planned blood sampling schedule; follow-up visit outranged from the time limits set up in the protocol due to plans/schedule of the participant etc.).
- Administrative deviations (e.g., change of the name).

In case of enrollment of the fewer number of subjects compared to that planned, CRO should inform the Sponsor who might approve of that. This should not be considered to be a protocol deviation. Notification and reporting of deviations from the protocol shall be submitted to the regulatory authorities and relevant Ethical Committees in compliance with the applicable requirements/instructions/laws.

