## **3.2** Serious protocol deviations

A serious protocol deviation (Item 11.3 of the trial protocol) is a deviation, which may, according to the estimate by the Investigator or a person assigned by the Investigator, result into withdrawal of the subject from the trial or withdrawal of his data from the statistical part of the trial. The deviations not referred to as serious ones shall be considered minor protocol deviations.

For the purposes of this analysis, the serious protocol deviations were defined as follows:

Description	Example/Explanation	Efficacy or safety	Excluded from population:
inclusion and non-	Inclusion criterion No. 5: e.g., inclusion of the patient with initial total TSS $< 5$	Efficiency	РР
Violation of the informed consent receipt procedure	Absence of the Informed Consent Form	Safety and efficacy	All

	Informed Consent Form was signed after randomization/initiation of therapy	Safety and efficacy	None
Randomization and study drugs	Prescription of the drug non-consitent with the randomization arm	Efficiency	РР
	Low compliance: the patient missed more than 3 doses of the study drug	Efficiency	РР
Concomitant drugs	The patient used prohibited drugs during the trial (or had used the drugs prohibited by the inclusion/exclusion criteria before the trial initiation)	Efficacy and safety	РР

A final list of serious protocol deviations will be compiled before the statistical analysis start. Every protocol deviation should be evaluated for the patient's exclusion from the PP data set or statistical analysis by the trial Sponsor representative. The decisions adopted and lists of patients included into the relevant data sets must be documented before the analysis initiation.

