## 3.3 Data sets for analysis

**The intention-to-treat (ITT) population:** All randomized subjects who have received at least one dose of the study drug/placebo and have completed at least one visit aimed at evaluation of the efficacy parameters (i.e., at least all the procedures of Visit 1).

According to the protocol (Section 9) and with reference to ICH E9 requirements, the ITT population will be considered to be a population for statistical analysis in the equivalence trials (including non-inferiority trials).

**The per protocol (PP) population:** All randomized subjects who have completed participation in the trial in accordance with the protocol (have completed the prescribed period of treatment and follow-up without significant deviations from the protocol).

A primary endpoint analysis will be conducted both for the ITT (main analysis) and PP populations (additional analysis).

Similarly, all efficacy endpoints will be analyzed both for the ITT and PP populations.

**The safety population (safety):** All randomized subjects who received at least one dose of the trial/reference drug and have completed at least one visit to the evaluation of the parameters of safety (i.e., at least all the procedures of Visit 1). As distinct from ITT population, the safety population will be analyzed depending on actually received treatment (not only prescribed) (in case of difference between the prescribed and received therapies).

The safety population will be used for all safety parameters including laboratory results, as well as for drug tolerability evaluation (see Section 2.3).

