## 3.10 Significance level

All statistical analyses in this trial will be conducted at 95% significance level (a threshold p value for confirmation of statistical significance is below 0.05), except for the primary endpoint where a one-sided statistical criterion will be used with 95% significance level (a threshold p value is below 0.05). The two-sided statistical criteria will be used for all other parameters.

For the primary endpoint evaluation, 90% CI will be calculated for the proportions difference with further evaluation of its lower boundary limit.

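### In this open trial, sponsor decisions on protocol deviations are not masked to arm or Day 4 outcome, and undefined wording in SAP 3.2 lets them reach beyond the PP set

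*SAP*

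**What the plan says.** **Who decides.** SAP 3.2 (Serious protocol deviations): "Every protocol deviation should be evaluated for the patient's exclusion from the PP data set or statistical analysis by the trial Sponsor representative". The final list of serious deviations is compiled, and set membership documented, before the statistical analysis starts. Protocol 11.3 allows the sponsor to move a deviation from minor to serious or back: "In such a case, the classification performed by the Sponsor shall prevail". The same sentence requires that the CRO be told, with a written rationale.

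**What is fixed in advance.** The SAP 3.2 table lists deviation types and the set each one leaves. Only an absent consent form removes a patient from all sets. Late consent removes the patient from none. Eligibility violations, wrong drug, more than three missed doses and prohibited drugs remove the patient from PP only.

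**Sets.** SAP 3.3 defines ITT by randomization, at least one dose and the Visit 1 procedures, with no deviation clause. "A primary endpoint analysis will be conducted both for the ITT (main analysis) and PP populations (additional analysis".

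**Blinding.** Protocol 4.3.2: "This trial will be conducted without blinding (an open trial". Protocol 4.8 has the sponsor keep the randomization list. Under SAP 3.7 the sponsor may choose to analyse Day 4 efficacy once at least 100 patients per arm have data. No section masks the deviation review.

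**The concern.** Open treatment does not require open data review. Under these rules the person who decides exclusions may know both the arm and whether the patient still had a sore throat on Day 4. The plan controls when the decision is recorded, not what the decider may see when making it. If an optional interim look has taken place, arm-level results could also be known before the list is closed.

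The discretion is not small. The SAP table treats more than three missed doses as a reason to leave PP. Protocol 6.3 says intake is as needed and that no lower limit of compliance is assessed. With no required dose count, whether a dose was missed is a matter of judgment.

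At stake are the credibility of the PP result as support for a non-inferiority claim and, through the undefined closing words of the SAP sentence, possibly the ITT result.

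**Working it through.** **Inputs.** 128 evaluable per arm, margin 14.5 points, expected rates 63% (comparator) and 65% (Angal) from Protocol 9.2; two-sided 90% Newcombe interval from SAP 4.1.2. The criterion is read as lower limit above −14.5 points, following the alternative hypothesis in SAP 3.9. The comparator count nearest 63% of 128 is 81 (63.3%).

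**The plan's own figure.** With the usual variance, n = (0.65×0.35 + 0.63×0.37) × ((1.960 + 0.842)/0.165)² = 0.4606 × 288.3 = 132.8, so 133 per arm, not 128. The protocol also plans at one-sided 2.5%, while SAP 3.10 says "a one-sided statistical criterion will be used with 95% significance level (a threshold p value is below 0.05". Both are separate issues. Here 128 is used only as the plan's evaluable number, and results are given for both interval levels.

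**Formula.** For p1 (Angal) and p2 (comparator), the lower limit is (p1 − p2) − √[(p1 − l1)² + (u2 − p2)²]. Here l1 and u2 are Wilson limits: [p + z²/2n ± z√(p(1−p)/n + z²/4n²)] / (1 + z²/n), with z = 1.645 for 90%.

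**One case in full.**
- Angal 75/128 = 0.5859, l1 = 0.5133. Comparator 81/128 = 0.6328, u2 = 0.6995.
- Lower limit = −0.0469 − √(0.0727² + 0.0667²) = −0.1455. This fails.
- Remove one Angal non-responder: 75/127 = 0.5906, l1 = 0.5176.
- Lower limit = −0.0423 − √(0.0729² + 0.0667²) = −0.1411. This passes.

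**Fewest Angal non-responders whose removal reverses the failure, comparator 81/128.**

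| Angal responders | 90% lower limit before removal | Removals needed |
|---|---|---|
| 75/128 | −14.55 | 1 |
| 74/128 | −15.33 | 2 |
| 73/128 | −16.11 | 4 |
| 72/128 | −16.89 | 6 |
| 70/128 | −18.45 | 10 |

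With a 95% interval, 77/128 needs 1, 76/128 needs 3 and 74/128 needs 6. At 140 per arm (comparator 88/140, 90% interval), 80, 79 and 78 responders need 2, 4 and 6.

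**Effect on error rates.** These come from exact binomial enumeration at 128 per arm, with k Angal non-responders always dropped. At the margin the true rates are 63% and 63 − 14.5 = 48.5%.

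| k dropped | False non-inferiority, 90% interval | False non-inferiority, 95% interval |
|---|---|---|
| 0 | 4.9% | 2.8% |
| 2 | 6.5% | 3.7% |
| 4 | 8.5% | 4.9% |
| 5 | 10.0% | 5.5% |

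Under the planned 65% against 63%, four such exclusions raise the pass rate with the 90% interval from 87.4% to 92.7%.

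**Text comparison for ITT.** The SAP 3.2 sentence allows exclusion from the statistical analysis without a criterion. The SAP 3.3 definition has no route out of ITT for a deviation, and the table has one, for absent consent. These cannot all hold as written.

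**The case against.** A reader might infer that a few unmasked exclusions could turn a failed trial into a non-inferiority claim. The documents do not support that.

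- ITT is the main analysis and has no deviation criterion, so PP exclusions cannot change the main conclusion. The only route to ITT is the phrase *or statistical analysis*, and the table above it suggests that absent consent may be all that was meant.
- The review is not purely case by case. The table fixes most categories, decisions must be documented before analysis, reclassification needs a written rationale, and Protocol 11.3 (with its documentation procedure) requires deviations to be reported promptly and described in the final report.
- No section says the representative sees Day 4 TSS. That is inferred from the open design and the absence of a masking rule.
- The counts assume every exclusion is an Angal non-responder and that the result just misses the margin. The 10% allowance in Protocol 9.2 does not show that such counts are ordinary. It concerns discontinuation, not deviations, and has already been removed to reach 128.
- Simply hiding all post-baseline TSS and lozenge counts would not work. Group B completion depends on total TSS ≤ 2 on Day 4, the missed-dose row needs counts, and Visit 3 exists only for Group B.

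All of this stands and limits the claim. It does not remove the gap: none of these safeguards restricts what the decider may see, the final list stays open until analysis, and the wider exclusion route has no stated criterion.

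**Conclusion.** The concern holds in a limited form. SAP 3.2 and Protocol 11.3 permit exclusions that depend on arm and outcome. PP, the additional analysis, is directly exposed. ITT is exposed only through three undefined words that contradict SAP 3.3 and the SAP 3.2 table.

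The possible effect is real but bounded: near the margin 1 to 4 exclusions suffice when the 90% result misses by one to three Angal responders, and four raise the error at the margin from 4.9% to 8.5%. These figures assume 128 per arm, a comparator rate near 63% and exclusions all in one direction, so they are a worst case and not a forecast. Nothing in the documents shows that selective exclusion is intended or that outcomes would in fact be consulted.

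**What to change.** 1. In SAP 3.2 delete *or statistical analysis*, and state that no deviation removes a patient from ITT except the absent-consent row of the table.
2. Derive rule-based items by program: eligibility, wrong drug, compliance, treatment completion (including the existing Group B Day 4 TSS ≤ 2 rule) and visit attendance. Pass them to the review only as yes/no flags that do not show arm, lozenge counts, Visit 3, or TSS and VAS values.
3. Decide the remaining judgment-based deviations, and any reclassification under Protocol 11.3, on listings without arm or post-baseline efficacy values. Sign the lists before database lock and before any interim look at efficacy by arm.
4. Reconcile the SAP missed-dose row with Protocol 6.3, so that the compliance flag in item 2 has one definition.

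The cost is SAP wording and some listing programming, with no extra patients or visits. Masking may remain incomplete for deviations that by their nature reveal the arm.

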## 3.3 Data sets for analysis

**The intention-to-treat (ITT) population:** All randomized subjects who have received at least one dose of the study drug/placebo and have completed at least one visit aimed at evaluation of the efficacy parameters (i.e., at least all the procedures of Visit 1).

According to the protocol (Section 9) and with reference to ICH E9 requirements, the ITT population will be considered to be a population for statistical analysis in the equivalence trials (including non-inferiority trials).

**The per protocol (PP) population:** All randomized subjects who have completed participation in the trial in accordance with the protocol (have completed the prescribed period of treatment and follow-up without significant deviations from the protocol).

A primary endpoint analysis will be conducted both for the ITT (main analysis) and PP populations (additional analysis).

Similarly, all efficacy endpoints will be analyzed both for the ITT and PP populations.

**The safety population (safety):** All randomized subjects who received at least one dose of the trial/reference drug and have completed at least one visit to the evaluation of the parameters of safety (i.e., at least all the procedures of Visit 1). As distinct from ITT population, the safety population will be analyzed depending on actually received treatment (not only prescribed) (in case of difference between the prescribed and received therapies).

The safety population will be used for all safety parameters including laboratory results, as well as for drug tolerability evaluation (see Section 2.3).

# 3.4 Subgroups

A subgroup analysis is not envisaged for this trial.

## 3.5 Data from various trial sites

This is a multicenter trial but data analysis for every particular trial site is not envisaged.

## 3.6 Missed data and outliers

At the database check, the expert in statistics authorized by the Sponsor and the data control and processing managers will analyze the trial results for questionable, missed and unanalyzable data, which will be the basis for the questions for investigators.

If possible, the investigators will eliminate the errors identified in CRFs and inform the Principal Investigator and authorized representatives of the Sponsor hereof. In case the identified data errors cannot be eliminated after the completion of the patients participation in the trial, the analysis of the resulting parameter sensitivity to questionable data will be conducted in the statistical analysis.

Information about the missed, questionable, and unanalyzable data will be summarized in the final clinical trial report.

The main analysis for the primary endpoint will be conducted without replacement for the missed, questionable, or unanalyzable data.

An additional analysis will be conducted with the data replacement (last observation carried forward); in this case, the last known TSS score will be carried to all subsequent control points.

All other data will be analyzed based on actually available information only, without data replacement.

Regarding abnormal test results, their clinical significance is evaluated by the Investigator during the trial with registration of AEs or adverse reactions, under control of the clinical trial specialists. Additional inquiries may be forwarded to the trial sites (before the cut-off date) if clinical significance of the abnormal test results is hard to evaluate.

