# 5.3 Exclusion criteria

#### 5.3.1 Terms and conditions for the subjects' exclusion from the trial

The subjects may be excluded from the trial on their own free will at any moment, without giving any reason, as well as upon decision of the Investigator or Sponsor in cases when continuation of the participation may inflict harm to the patient's health and/or life. In addition, the patient must be excluded in the cases listed below:

- 1. Negative course of the disease with signs of the secondary bacterial infection (including body temperature increase above 37.5 °C).
- 2. The Ethics Committee, regulatory authorities, or Sponsor terminate the trial or participation of the specific trial site for any reason.
- 3. The Investigator's decision to withdraw the patient from the trial in the interests of the patient.
- 4. Withdrawal of the informed consent (unwillingness of the patient to continue his/her participation in the trial).
- 5. Serious deviation from the trial protocol.
- 6. Individual intolerance of the study drugs.
- 7. Clinically significant adverse event or serious adverse event.
- 8. Patient's non-compliance.
- 9. False inclusion (e.g., the patient was included in breach of the inclusion/non-inclusion criteria).
- 10. The patient complies with the non-inclusion criteria during the trial.
- 11. The patient receives or requires an additional therapy which might influence the trial results or patient's safety (see *Prohibited concomitant therapy* section).

12. Other conditions or events which, in the Investigator's opinion, require the patient's exclusion from the trial.

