#### 7.2 Methods and timing for evaluation, recording, and analysis of efficacy parameters

The methods for efficacy criteria evaluation are described in Section 4.2.3.2. The first endpoint is evaluated in the morning at Visit 2 (Day 4, after 3 days of the trial therapy) before the study drugs intake. Other efficacy endpoints are evaluated in terms stated in Section 7.1.

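### Patients withdrawn before Day 4 for worsening or added therapy have no stated outcome in the main ITT analysis, and the SAP's missed-dose rule for PP contradicts the protocol

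*SAP*

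**What the plan says.** **Missing outcomes.** For the main analysis, SAP 3.6 and Protocol 9.5 both say: "The main analysis for the primary endpoint will be conducted without replacement for the missed, questionable, or unanalyzable data". In an additional LOCF analysis, "the last known TSS score will be carried to all subsequent control points".

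**Populations.** ITT is the main population. It needs one dose and the Visit 1 procedures, not a Day-4 assessment (Protocol 9.7, SAP 3.3). PP patients must "have completed the prescribed period of treatment and follow-up without significant deviations from the protocol".

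**Timing.** Protocol 7.2: "The first endpoint is evaluated in the morning at Visit 2 (Day 4, after 3 days of the trial therapy", before that day's drug intake.

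**Withdrawal.** Protocol 5.3.1 says that "the patient must be excluded in the cases listed below", among them "Negative course of the disease with signs of the secondary bacterial infection" and "The patient receives or requires an additional therapy which might influence the trial results or patient's safety". The synopsis is softer: its exclusion criteria say that a patient may be excluded on these grounds, and its text on worsening leaves early discontinuation to the investigator.

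**TSS before Day 4.** A premature-discontinuation visit uses Visit 2 procedures (Protocol 4.2.4.6, SAP 3.8.6), and Table 1 lists TSS at Visit 2. Unscheduled visits include TSS (Protocol 4.2.4.5, SAP 3.8.5). A patient who refuses to come is telephoned (Protocol 5.3.1.1).

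**Prohibited drugs.** SAP 3.2 lists "The patient used prohibited drugs during the trial" as a reason for exclusion from PP only.

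**Compliance.** SAP 3.2 also removes from PP a patient who missed more than three doses. Protocol 6.3 says that both drugs are taken when needed, that no lower limit of compliance will be assessed, and that use is compared with the maximum amounts. SAP 1 says that it envisages no changes from the protocol.

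**The concern.** **(a) Main analysis.** The two quoted withdrawal reasons are close to the opposite of the endpoint, which is absence of sore throat. A patient withdrawn on Day 2 or 3 for either reason is in ITT by definition but is not in the denominator of the proportion that decides the trial. PP leaves the same patient out, so the two prespecified populations do not check each other on this point. Patients and investigators know the treatment, and part of the decision to withdraw is judgement, so equal withdrawal in the two arms cannot be taken for granted. At stake is the one confirmatory conclusion.

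**(b) PP set.** With as-needed intake there is no reference count from which a dose can be missed. A patient who took few lozenges because the pain resolved early could be removed from PP as non-compliant. Only the supporting analysis is affected.

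**Working it through.** **Inputs.** From the documents: margin 14.5 points, two-sided 90% Newcombe interval, expected comparator rate 63%, 140 randomised per arm. I read the decision rule as lower limit above -14.5%, in line with the stated hypotheses. Assumed: all loss rates and the share of losses that are failures. The documents give only a 10% discontinuation rate for the treatment period, which covers all causes and so is an upper range for this type of loss.

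**Method.** Put the true difference at the margin among all randomised patients: pA = 63% - 14.5% = 48.5%, pB = 63%. Let w be the proportion lost in an arm and f the share of those lost who are failures. If they are omitted, the expected rate among those left is

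q = (p - (1 - f)w) / (1 - w), with arm size 140(1 - w), rounded.

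The claim rate is the exact sum of binomial probabilities over all outcomes whose Newcombe lower limit exceeds -14.5%.

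**All losses are failures (f = 1, so q = p/(1 - w)).**

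| Loss, Angal v comparator | Evaluated | Expected rates | Difference (points) | False-claim rate |
|---|---|---|---|---|
| Counted as failures | 140 v 140 | 48.5% v 63.0% | -14.5 | 4.9% |
| 5% v 5%, omitted | 133 v 133 | 51.1% v 66.3% | -15.3 | 4.1% |
| 10% v 10%, omitted | 126 v 126 | 53.9% v 70.0% | -16.1 | 2.8% |
| 12% v 8%, omitted | 123 v 129 | 55.1% v 68.5% | -13.4 | 7.6% |
| 8% v 12%, omitted | 129 v 123 | 52.7% v 71.6% | -18.9 | about 1% |

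**Only some losses are failures, 12% v 8%.** At f = 0.5, qA = (0.485 - 0.06)/0.88 = 48.3% and qB = (0.63 - 0.04)/0.92 = 64.1%, a difference of -15.8 points. The claim rate is 3.3%. It is 4.7% at f = 0.70, 5.1% at 0.75 and 5.6% at 0.80, so it passes 4.9% at roughly f = 0.73.

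**Borderline results, with 88 comparator responders.**
- 80/140 v 88/140 gives a lower limit of -15.2% (fail). Omitting two Angal failures, 80/138 v 88/140 gives -14.4% (pass).
- 81/140 v 88/140 gives -14.46% (pass). Omitting two failures per arm, 81/138 v 88/138 gives -14.56% (fail).

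**Link to the margin.** The source trial left out two unknown outcomes in its active arm. The unpooled normal 90% interval for 65/104 v 38/103 is 0.2561 - 1.645 × 0.0672 = 14.56%, which reproduces the protocol's figure. With the two scored as failures, 65/106 gives 0.2443 - 1.645 × 0.0671 = 13.40%.

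**Part (b)** needs no arithmetic: SAP 3.2 applies a lower compliance threshold, and Protocol 6.3 says that none will be evaluated.

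**The case against.** **A TSS will usually exist.** Worsening that leads to discontinuation calls for an unscheduled visit, and both types of early visit record TSS. This stands as to data collection. But neither document says that the early value is the Day-4 endpoint, and using it in the main analysis would be a carry-forward, which that analysis rules out. A patient reached only by telephone has no investigator score at all.

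**LOCF already covers it.** Largely true. Throat pain is an entry condition, so a worsening patient would nearly always be carried forward as not resolved. What remains is that LOCF does not decide the result.

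**The present rule matches the source trial.** It does: 65/104 also leaves out unknown outcomes. The reasons for those two are not given.

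**The flips are chosen at the boundary.** They are. They show only that a few patients can matter in a close result.

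**Readings that go too far.** A reader might infer that omission generally favours Angal. It does not: equal loss is conservative, more loss on the comparator is strongly conservative, and even 12% v 8% inflates error only if about three quarters of the losses are failures. A reader might infer that withdrawal is mandatory throughout; the synopsis makes it discretionary. A reader might also infer that nothing governs prohibited-drug users who attend Day 4. Under the plan they are scored as observed in ITT and removed from PP.

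**On (b)**, the final deviation list and the case-by-case review before analysis soften the rule, but they do not define a missed dose.

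**Conclusion.** (a) The main ITT analysis gives no outcome to patients withdrawn before Day 4 for reasons that amount to treatment failure, and the status of an early TSS is not stated. This is a cheap improvement to make, not a demonstrated bias. Its direction and size depend on the split between arms. Against 4.9% with failures counted, omission gives 2.8% at equal 10% loss, 7.6% at 12% v 8% and about 1% at 8% v 12% when every loss is a failure, but 3.3% at 12% v 8% when only half are. All loss rates and failure shares are assumptions; the documents do not support any particular imbalance.

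(b) The missed-dose rule in SAP 3.2 is wrong as written, because it contradicts Protocol 6.3 while the SAP claims no change from the protocol. It affects only the supporting PP analysis, and its effect was not quantified.

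**What to change.** **Protocol 9.5 and SAP 3.6**
- In the main ITT analysis, count patients withdrawn before the Day-4 assessment for worsening, or for prohibited analgesic or antibacterial therapy, as sore throat not resolved.
- State that an earlier TSS is not the Day-4 value.
- Keep the available-data and LOCF analyses as sensitivity analyses.
- Add a sensitivity analysis that scores prohibited-therapy users who attend Day 4 as not resolved.
- Report withdrawals before Day 4 by reason and arm.

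**Protocol 5.3.1 and synopsis.** Reconcile the mandatory and discretionary wording on exclusion.

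**SAP 3.2 and Protocol 6.3.** Reconcile them, by deleting the missed-dose row or replacing it with the comparison against maximum amounts that Protocol 6.3 already specifies.

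**Cost.** Wording only; no new data. Response rates will read slightly lower. Power is hardly touched when loss is equal: with 65% v 63% among completers and 10% of each arm lost as failures, it is 86.9% counted and 86.5% omitted (90% interval). The convention would differ from the one behind the margin. The protocol should acknowledge this and note that 14.56% would become 13.40% if the source trial's two unknown outcomes were scored as failures.
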